3.5.3 Exploratory Efficacy Endpoints

Time to event endpoints will be tested with a two-sided stratified log rank test using the randomization stratification factors BCVA ETDRS letter score (64 letters or better vs. 63 letters or worse) and previous macular laser treatment as strata. Kaplan Meier curves will be displayed, and median time to event estimates will be computed.

Effect modification will be tested in the overall (treatment-naïve and previously treated combined) ITT population by adding a previous IVT anti-VEGF treatment status and a treatment arm by visit by previous IVT anti-VEGF treatment status interaction terms to the Linear model described in section 3.5.1. The treatment arm by visit by previous IVT anti-VEGF treatment status interaction term will be tested at a 10% significance level.

3.5.4 Sensitivity Analyses

Effects of prognostic factors on the BCVA change from baseline will be investigated using the MMRM model described in section 3.5.1. The measurement at BL (baseline) of each of the following variables may be used as covariates in the model:

- Age

RO6867461—F. Hoffmann-La Roche Ltd
Statistical Analysis Plan BP30099

3.5.5 Subgroup Analyses

For the sub-group analysis the MMRM for change from baseline in BCVA will be used in the following subgroups defined at baseline:

- Previous macular laser treatment (from eCRF)
- Gender
- BCVA strata (64 letters or better vs. 63 letters or worse, from eCRF).
- BCVA Categories at BL (20/40 or better, 20/200 or better),

The sub-group analyses will be performed separately in each sub-group.

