4.2 STUDY POPULATION

4.2.1 Inclusion Criteria

Patients must meet the following criteria for study entry:

Ocular criteria for study eye:

- Macular edema associated with DR defined as macular thickening by spectral domain optical coherence tomography (SD-OCT) involving the center of the macula: CST of $\geq 325\mu\text{m}$ with Spectralis (Heidelberg) at screening (where Spectralis is not available, the following devices and CST thresholds are acceptable: CST $\geq 315\mu\text{m}$ for Cirrus, CST $\geq 315\mu\text{m}$ for Topcon, CST $\geq 295\mu\text{m}$ for Optovue)
- Decreased VA attributable primarily to DME, with BCVA letter score of 73–24 letters (inclusive) on ETDRS-like charts (20/40–20/320 Snellen equivalent) on Day 1
- Clear ocular media and adequate pupillary dilatation to allow acquisition of good quality retinal images to confirm diagnosis

General criteria:

- Diagnosis of diabetes mellitus (DM; Type 1 or Type 2), as defined by the World Health Organization and/or American Diabetes Association
- Able and willing to provide written informed consent and to comply with the study protocol according to International Conference on Harmonisation (ICH) and local regulations. Alternatively, a legally authorized representative must be able to consent for the patient according to ICH and local regulations.

RO6867461—F. Hoffmann-La Roche Ltd
34/Protocol BP30099, Version 3

- Age ≥ 18 years
- For women who are not postmenopausal (i.e. ≥ 12 months of non-therapy-induced amenorrhea, confirmed by FSH, if not on hormone replacement) or surgically sterile (absence of ovaries and/or uterus) agreement to remain abstinent or use combined contraceptive methods that result in a failure rate of $< 1\%$ per year during the treatment period and at least through 4 weeks after last dose.

Abstinence is only acceptable if it is in line with the preferred and usual lifestyle of the patient. Periodic abstinence (e.g., calendar, ovulation, symptothermal, or postovulation methods) and withdrawal are not acceptable methods of contraception.

Examples of contraceptive methods with an expected failure rate of $< 1\%$ per year include male sterilization, hormonal implants, proper use of combined oral or injected hormonal contraceptives, and certain intrauterine devices.

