1.2.3.2 Secondary Efficacy Outcome Measures

The secondary efficacy outcome measures include functional (BCVA) and anatomical (PD imaging) measures relevant to the mechanism of action of RO6867461 as follows:

BCVA:

- Proportion of patients gaining ≥ 15 letters from baseline BCVA at Week 24
- Proportion of patients with BCVA ≥ 69 letters (20/40 or better) at Week 24
- Proportion of patients with BCVA ≥ 84 letters (20/20 or better) at Week 24

Anatomic outcome measures by SD-OCT:

- Mean change from baseline in foveal center point thickness at Week 24
- Mean change from baseline in mean CST (1 mm diameter) at Week 24
- Proportion of patients with resolution of subretinal and intraretinal fluid at Week 24

Anatomic outcome measures by FFA:

- Proportion of patients with resolution of leakage at the macula at Week 24
- Change from baseline in the size of the foveal avascular zone at Week 24

Table 1 Description of Secondary Outcome Measures

Secondary EndPoint	Detailed Definition	Variable names used by central reading center
Foveal Center Point thickness (Central Foveal Thickness)	Thickness from Inner Limiting Membrane to the Retinal Pigment Epithelial at the horizontal slice closest to the center of the fovea	OCTCentralRetinalThickness1-3
mean CST	Mean thickness from Inner Limiting Membrane to the Retinal Pigment Epithelial over the 1 mm central subfield	OCTCentralSubfieldThickness1-3
intra-retinal fluid (IRF)	Presence of fluid within the retina	OCTIntraRetinalFluid
sub-retinal fluid SRF)	Presence of fluid between the retina and the retinal pigment epithelium	OCTSubretinalFluidThicknessNotPresent
Resolution of leakage at the macula	Resolution of fluorescein leakage at the macula	FAMaculaMLEakageArea1-3 or FAMaculaMLEakage
Size of the foveal avascular zone	Size of the foveal avascular zone (FAZ) by FFA	FAMaculaFAZArea1-3 FAMaculaFAZAreaB1-3

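### SAP 3.5.5 defines nested baseline-acuity categories that omit eyes worse than 20/200, and no subgroup factor listed there gets an estimated difference in treatment effect

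*SAP*

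**What the plan says.** SAP 3.5.5 applies the primary repeated-measures model (MMRM) for change in BCVA to subgroups defined by four baseline factors: previous macular laser treatment, gender, "BCVA strata (64 letters or better vs. 63 letters or worse, from eCRF", and "BCVA Categories at BL (20/40 or better, 20/200 or better". It then states: "The sub-group analyses will be performed separately in each sub-group". No treatment-by-subgroup term is specified for any of the four.

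Eligibility (Protocol 4.2.1) requires a "BCVA letter score of 73–24 letters (inclusive) on ETDRS-like charts (20/40–20/320 Snellen equivalent) on Day 1". Elsewhere the SAP ties Snellen values to letter scores. The secondary endpoints in 1.2.3.2 include "Proportion of patients with BCVA ≥ 69 letters (20/40 or better) at Week 24" and "Proportion of patients with BCVA ≥ 84 letters (20/20 or better) at Week 24".

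The SAP does plan one interaction test, for a factor that is not in the 3.5.5 list. In 3.5.3: "The treatment arm by visit by previous IVT anti-VEGF treatment status interaction term will be tested at a 10% significance level". SAP 3.5.2 adds that baseline parameters will be examined as covariates and in subgroup analysis, but it names no interaction term.

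**The concern.** There are two separate problems.

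- **The category line.** Both categories are cumulative from the top of the acuity scale. Every eye in the better category is also in the wider one, so their two estimates share patients and are not a comparison of independent groups. The eyes with the worst eligible vision appear in neither. The line directly above it states both sides of its split; this one does not.
- **Separate fits.** For every factor, the planned output is one treatment effect and one p-value per subgroup. That output does not show whether the effects differ. Adding a baseline factor as a covariate does not show it either, because a main effect adjusts the mean and leaves the treatment effect common.

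What is at stake is the reading of exploratory results. Protocol 6.11 says the efficacy looks are meant to inform future development options. A pattern such as a positive result in one acuity group and not in the other could feed those choices, although chance alone produces it often.

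**Working it through.** **Step 1: letter ranges.** The documents give 20/20 = 84 letters, 20/40 = 69 letters and 20/320 = 24 letters (SAP 1.2.3.2, Protocol 4.2.1). The scale 84 − 50 × log10(denominator/20) gives 68.9 for 20/40 and 23.8 for 20/320, which round to the documents' own values. For 20/200 it gives 84 − 50 × log10(10) = 34. The documents do not state this last value; it is interpolated on their scale.

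- 20/40 or better: 69–73, which is 5 of the 50 eligible scores.
- 20/200 or better: 34–73, which is 40 of 50 and contains all of the first group.
- In neither: 24–33, which is 10 of 50. All of these fall in the 63-or-worse stratum, so they are included in that split.

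These are counts of possible scores, not shares of patients. The documents give no patient shares.

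**Step 2: reproduce the plan's power.** SAP 1.3 gives 50 treatment-naïve patients per arm, 10% drop-out (45 evaluable), SD 11, a difference of 5 letters and one-sided 10%.

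- SE = 11 × √(2/45) = 2.32.
- Power = Φ(5/2.32 − 1.2816) = 0.809, against 80% stated.
- Minimum detectable difference = 1.2816 × 2.32 = 2.97, against about 3 stated.

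**Step 3: separate fits, one dose against Arm A, same true effect of 5 letters in both subgroups.** For two equal halves:

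- SE = 11 × √(2/22.5) = 3.28 in each half.
- Power = Φ(5/3.28 − 1.2816) = 0.596 in each half.
- The halves share no patients, so P(exactly one positive) = 2 × 0.596 × 0.404 = 0.48.

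**Step 4: the difference in effects between two disjoint subgroups.** SE = √(SE₁² + SE₂²). For equal halves this is √(3.28² + 3.28²) = 4.64. The test is taken at two-sided 10%, the level SAP 3.5.3 uses for its one interaction test. All splits below are assumptions.

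| Split | SE in each | Power in each | Exactly one positive | SE of difference | 80% CI half-width | Power for a 5-letter difference | Difference with 80% power |
|---|---|---|---|---|---|---|---|
| 50/50 | 3.28, 3.28 | 0.596, 0.596 | 0.482 | 4.64 | 5.9 | 29% | 11.5 |
| 30/70 | 4.23, 2.77 | 0.460, 0.699 | 0.516 | 5.06 | 6.5 | 26% | 12.6 |
| 20/80 | 5.19, 2.59 | 0.376, 0.741 | 0.560 | 5.80 | 7.4 | 22% | 14.4 |
| 10/90 | 7.33, 2.44 | 0.274, 0.778 | 0.625 | 7.73 | 9.9 | 17% | 19.2 |

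These are normal approximations for a comparison of two means, as in the SAP's own sample-size statement. The 10/90 row rests on about 4.5 patients per arm in the smaller subgroup and is only indicative.

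**Step 5: what these figures do not cover.** Steps 3 and 4 apply to disjoint groups and do not measure the nesting fault. For nested groups the two estimates are correlated at about √(n_small/n_large), for example √(0.10/0.90) = 0.33 if the shares were 10% and 90%.

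**The case against.** The strongest reply has four parts.

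- **The line may be shorthand.** It could mean two cut-points, each taken as or-better against worse, and it ends on a comma as if unfinished. SAP 3.5 also refers to a separate List of Planned Outputs, which may settle it. This is possible, but the SAP does not say so. Two programmers could build different tables from this line, so it needs rewording on either reading.
- **The fault is confined to one line.** This stands. Laser, gender and the 64/63 strata are disjoint and exhaustive. A reader might infer that none of the subgroup results can be interpreted; the documents do not support that. For these three factors anyone can contrast the two estimates using √(SE₁² + SE₂²). A reader might also infer that eyes worse than 20/200 are absent from every acuity subgroup; they are in the 63-or-worse stratum.
- **No misuse is planned.** This also stands. SAP 3.5.5 sets no decision rule and does not propose to compare significance across subgroups. SAP 3.8 calls the study hypothesis-generating, and an interaction test is planned for prior anti-VEGF treatment, the one modifier that is a stated exploratory objective. The risk lies in how the output would be read, and the plan makes no claim of effect modification.
- **An interaction test would be weak.** This is correct, at about 17–29% power for a 5-letter difference. It argues for reporting the difference with its interval and against relying on a p-value. It does not favour separate p-values, which conceal the same imprecision.

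**Conclusion.** The point holds in a limited form and is minor. As written, the baseline BCVA categories are nested and leave eligible eyes at about 24–33 letters in neither group. The lower limit of 34 letters for 20/200 rests on interpolation between the documents' own anchors.

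For all four factors, no difference in treatment effect is planned to be estimated, so separate significance results must not be read as effect modification. With a true effect of 5 letters everywhere, SD 11 and 45 evaluable patients per arm, exactly one of two equal halves is positive about 48% of the time, and more often if the split is unequal. The equal split is an assumption, and the figure is a general consequence of halving a trial of this size. It should not be quoted as the size of the nesting fault. The primary analysis is untouched.

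**What to change.** **Category line.** Replace it with mutually exclusive letter bands covering 24–73 letters, for example 69–73, 34–68 and 24–33, with a stated rule for merging sparse bands. Alternatively, state two separate splits: 20/40 or better against worse, and 20/200 or better against worse. Give the cut-points in letters.

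**Model.** For each factor, fit one MMRM in the treatment-naïve patients with treatment-by-visit-by-subgroup terms and the lower-order terms they need. Report each subgroup's Week 24 effect and the Week 24 difference in effects for each dose against Arm A, with 80% CIs as in SAP 3.5.1. Label all of it exploratory, and state that significance in one subgroup but not another is not evidence of a different effect.

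**Cross-reference.** In the same edit, correct SAP 3.5.2, which sends the reader to section 4.4.5 for this analysis; the subgroup section is 3.5.5.

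**Cost.** A few lines of SAP text and about one interaction model per factor. The intervals will be wide: with equal halves the 80% CI is about ±5.9 letters, and 80% power needs a difference in effect of 11.5 letters. The output is an estimate with its uncertainty and not a decisive test. No change to data collection or sample size is needed.

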3.6 SAFETY ANALYSES

All safety analyses will be based on the safety analysis population. The LoPO contains the full list of reports for safety analyses.

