2.3 EXPLORATORY OBJECTIVES

The exploratory objectives for this study are as follows:

- *To explore the predictive effect of previous IVT anti-VEGF treatment on efficacy of RO6867461*
- *To evaluate the efficacy and safety of RO6867461 compared with the active comparator in patients with CI-DME with previous IVT anti-VEGF treatment.*
- 

- [REDACTED]
- [REDACTED]
- [REDACTED]
- To evaluate improvement in DR severity score

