3.1.2 Number of Patients

Up to 210 patients will be randomized. Approximately 150 treatment-naïve patients and approximately 60 patients who have been previously treated with IVT anti-VEGF will be enrolled in the study. Approximately 50 treatment-naïve patients will be randomized

RO6867461—F. Hoffmann-La Roche Ltd
28/Protocol BP30099, Version 3

into each arm (1:1:1 randomization scheme) and approximately 30 patients previously treated with IVT anti-VEGF will be randomized into arms A and C.

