4.3 METHOD OF TREATMENT ASSIGNMENT AND MASKING

4.3.1 Treatment Assignment

After written informed consent has been obtained, all patients will receive a screening number assigned through the interactive voice and web response system (IxRS).

A patient must satisfy all eligibility criteria (see Section 4.2.1 and Section 4.2.2) at the screening or Day 1 visit (as defined for each individual criterion in Section 4.2 and below) prior to randomization and first study treatment (see Section 4.6.7.1). As part of the screening process, FP, FFA, and SD-OCT will be transferred to the central reading center, and a set of images will be evaluated to provide an objective, masked assessment of certain eligibility criteria.

Only one eye will be selected as the study eye. See Section 4.6.7.1 for details.

After all patient eligibility requirements are confirmed on Day 1 visit (see Section 4.2), including:

- Baseline BCVA letter score of 73 to 24 letters (inclusive) in the study eye
- Absence of active intraocular inflammation in the study eye
- Absence of febrile illness within one week prior to Day 1,

the site personnel will contact the IxRS for assignment of a patient identification number (a separate number from the screening number).

Treatment naïve patients will be randomized in a 1:1:1 ratio to one of the arms A, B and C, respectively. Patients previously treated with IVT anti-VEGF will be randomized in a 1:1 ratio to arms A and C.:

- Arm A: 0.3 mg ranibizumab IVT
- Arm B: 1.5 mg RO6867461 IVT

RO6867461—F. Hoffmann-La Roche Ltd
37/Protocol BP30099, Version 3

- Arm C: 6 mg RO6867461 IVT

This study will consist of a treatment period (20 weeks) and an observational period (up to 16 weeks), for a total study length of up to 36 weeks. During the treatment period, the study drug will be administered to the patients on Day 1 and on every 4th week, for a total of 6 injections. During the observational period, patients will be evaluated every 4th week. If during any of these evaluations the patients meet the pre-specified criteria (see Section 4.3.1.1), the patients will receive a single dose of 0.3 mg ranibizumab and exit the study. They will receive a follow up phone call 7 days after the dose of ranibizumab to evaluate any potential adverse events. Otherwise, patients will exit the study once they have completed the observational visit at week 36.

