3.1.1 Safety Analysis Population

All patients who have received at least one dose of the study drug, whether prematurely withdrawn from the study or not, will be included in the safety analysis. Patients will be grouped according to the actual treatment received.

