3.3 ANALYSIS OF TREATMENT GROUP COMPARABILITY

Demographics, baseline characteristics (including ocular assessments, patient disposition, and medical history), and all baseline laboratory values will be summarized descriptively by treatment arm and previous anti-VEGF treatment status using frequency tables and summary statistics providing means, medians, standard deviations, first and third quartiles, and extreme values.

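### No safety summary by previous anti-VEGF status is specified, so Arms A and C (about 37.5% previously treated) are tabulated beside an all-naive Arm B

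*SAP*

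**What the plan says.** **Safety set.** Protocol 6.6 and SAP 3.6 carry the same rule: "All safety analyses will be based on the safety analysis population". SAP 3.1.1 defines that population as "All patients who have received at least one dose of the study drug, whether prematurely withdrawn from the study or not", and adds: "Patients will be grouped according to the actual treatment received". SAP 3.6 then refers to the LoPO for the complete set of safety reports. That list is not part of the protocol or SAP.

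**Allocation.** Protocol 3.1.2 plans for "Approximately 150 treatment-naïve patients and approximately 60 patients who have been previously treated with IVT anti-VEGF". Under protocol 4.3.1, "Treatment naïve patients will be randomized in a 1:1:1 ratio to one of the arms A, B and C, respectively", whereas "Patients previously treated with IVT anti-VEGF will be randomized in a 1:1 ratio to arms A and C". No previously treated patient can be assigned to Arm B.

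**Objective.** Protocol 2.3 lists, as exploratory, "To evaluate the efficacy and safety of RO6867461 compared with the active comparator in patients with CI-DME with previous IVT anti-VEGF treatment".

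**Use of previous anti-VEGF status elsewhere.** The SAP uses it for baseline data, "summarized descriptively by treatment arm and previous anti-VEGF treatment status" (SAP 3.3, similarly 3.2), for separate intent-to-treat populations (SAP 3.1.2) and for separate efficacy analyses (SAP 3.5). SAP 3.6.1 to 3.6.8 and protocol 6.6.1 to 6.6.7 do not mention it. Adverse events are split into systemic and ocular and by eye, and concomitant medications into ocular and non-ocular. SAP 3.6.5 tabulates anti-drug antibodies for every arm except A.

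**The concern.** Descriptive safety tables are read by comparing columns, with no model to adjust for who is in each column. Followed as written, the tables set an all-naive 1.5 mg arm beside a 6 mg arm and a ranibizumab arm that each contain a sizeable previously treated fraction. If event rates differ between naive and previously treated patients for reasons unrelated to study drug, part of any difference between B and C, or B and A, reflects patient mix.

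Three places are most exposed:

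- **Dose.** B versus C is the trial's only randomized comparison of the two RO6867461 doses, and protocol 1.2.2 reports no earlier clinical data in DME.
- **Antibodies.** With Arm A left out, the only columns are B and C, so the one pair of arms with matching mix is not available. Antibody formation is a secondary objective.
- **BCVA.** SAP 3.5 analyzes naive and previously treated patients separately and makes the pooled repeat of the primary analysis conditional on no strong evidence of effect modification. SAP 3.6.6 tabulates BCVA change in the safety population with no such condition.

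Separately, the safety half of the protocol 2.3 objective has no analysis described in either text.

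**Working it through.** **The plan's own figures.** The stated sample size concerns efficacy in naive patients only. With 50 × 0.9 = 45 per arm, SD 11, a difference of 5 letters and one-sided alpha of 10%, the standard error is 11 × √(2/45) = 2.319, and power is Φ(5/2.319 − 1.2816) = 0.809, which agrees with the stated 80%. The minimum detectable difference is 1.2816 × 2.319 = 2.97, which agrees with about 3. No figure is given for safety or for the previously treated stratum, and nothing below changes the sample size.

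**Planned mix** (protocol 3.1.2 and 4.3.1). About 150 naive patients split three ways gives 50 per arm; about 60 previously treated split two ways gives 30 each in A and C.

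| Arm | Naive | Previously treated | Total | Share previously treated |
|---|---|---|---|---|
| A | 50 | 30 | 80 | 37.5% |
| B | 50 | 0 | 50 | 0% |
| C | 50 | 30 | 80 | 37.5% |
| All | 150 | 60 | 210 | 28.6% |

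The figure of about 30 has to mean 30 per arm: 30 in all would give 150 + 30 = 180, not the stated 210.

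**Shift from mix alone.** Let p_n be the event rate in naive patients and p_t the rate in previously treated patients, the same in every arm (no drug effect).

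- Arm A or C: (50 p_n + 30 p_t)/80 = p_n + 0.375 (p_t − p_n)
- Arm B: p_n
- A or C minus B: 0.375 (p_t − p_n)

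The documents give no rates by previous treatment, so the gap is an assumption:

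| Assumed gap p_t − p_n | Shift, A or C minus B |
|---|---|
| 2 points (for example 4% v 2%) | 0.75 points |
| 5 points | 1.9 points |
| 10 points | 3.75 points |
| 20 points | 7.5 points |

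A negative gap reverses the sign. For example, p_n = 30% and p_t = 40% gives 33.75% in A and C against 30% in B; p_n = 30% and p_t = 20% gives 26.25% against 30%. The weight of 0.375 also applies to mean changes such as BCVA or IOP. A and C have the same planned mix, so A minus C is 0.

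**Set against sampling error.** The 95% half-width for a difference between 80 and 50 patients is 1.96 × √[p(1 − p)(1/80 + 1/50)], which is 10.6 points at an assumed rate of 10% and 16.2 at 30%. Mix is therefore usually smaller than noise, but it is systematic and can be removed.

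**After the split.** Naive columns are 50/50/50, and the difference in mix against Arm B falls from 37.5 points to 0. Half-widths for 50 v 50 are 11.8 and 18.0 points at the same rates. Previously treated columns are 30/30: the half-width is 15.2 points at 10% and 23.2 at 30%, and 0 events in 30 leaves a one-sided 95% upper bound of 1 − 0.05^(1/30) = 9.5%.

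**The case against.** The strongest reply is that a population is not a table layout. The SAP sentence fixes who is included, and the grouping sentence is an as-treated rule; neither forbids a further split. A table by arm and previous status would still rest on the safety population, and the LoPO may already list such tables. This stands. A reader might infer that the objective in previously treated patients will receive no safety analysis, or cannot be answered. The documents do not support that: they show only that the protocol and SAP text specify none. Equally, deferral to the LoPO does not explain the omission, because SAP 3.5 also defers its full output list to the LoPO and still states the efficacy split in the text.

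It is also fair that no B-versus-C safety test or dose-trend claim is planned, that the outputs are descriptive, and that protocol 6.10 allows exploratory analyses against nominal dose or concentration. Individual listings of laboratory, vital-sign and ECG values are not affected by mix. Baseline tables will show the imbalance. Both strata face the same eligibility criteria, including no anti-VEGF in the study eye within 3 months before Day 1, so a large gap in rates is not established. These points limit the weight of the finding. They do not make the columns comparable.

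A reader might go further and conclude that Arm B should be removed from the all-patient tables. Nothing in the documents requires that; it would drop a randomized arm from the all-treated display.

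**Conclusion.** The point holds as a gap in specification with a definite consequence. As the text stands, safety comparisons that involve Arm B mix dose or drug with patient mix, by 0.375 times the gap in rate between previously treated and naive patients: 3.75 points for an assumed 10-point gap and 7.5 for 20, in either direction. The 37.5% rests on the planned allocation; the gaps are assumptions. The exploratory safety objective in previously treated patients has no analysis specified in the protocol or SAP, and the LoPO could not be checked.

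The size is modest against sampling error, and uncommon events are shifted very little. It would be too strong to say that the safety analyses as a whole are confounded or that the safety population is wrongly defined: A versus C keeps the same planned mix, and the population is a conventional all-treated one. What is missing is a split by a factor that the trial already randomizes by and already uses for baseline and efficacy. This is a cheap improvement.

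**What to change.** Add to SAP 3.6:

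1. Key safety summaries (adverse events, serious adverse events, ocular adverse events, anti-drug antibodies, BCVA, IOP) are also produced for treatment-naive patients (Arms A, B and C; antibodies B and C) and for previously treated patients (Arms A and C; antibodies C only).
2. Any statement comparing Arm B with A or C, including any on dose and safety, is based on the naive tables.
3. All-patient tables keep all three arms, with a footnote giving the number previously treated in each column.

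Bring the LoPO into line. No new data, visits or sample-size change are needed. The cost is more tables and smaller denominators, about 50 per arm in naive patients and about 30 per arm in previously treated patients. The latter tables will be descriptive only.
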